### 16.6 Eastern Cooperative Group Performance Status

Grade	ECOG Performance Status
0	Fully active, able to carry on all pre-disease performance without restriction
1	Restricted in physically strenuous activity but ambulatory and able to carry out work of a light or sedentary nature, e.g., light house work, office work
2	Ambulatory and capable of all self-care but unable to carry out any work activities; up and about more than 50% of waking hours
3	Capable of only limited self-care; confined to bed or chair more than 50% of waking hours
4	Completely disabled; cannot carry on any self-care; totally confined to bed or chair
5	Dead

### 16.7 Revised IWG-MRT and ELN Response Criteria for MF

Response categories	Required criteria (for all response categories, benefit must last for ≥12 weeks to qualify as a response)
CR	Bone marrow:* Age-adjusted normocellularity; <5% blasts; ≤grade 1 MF † and
	Peripheral blood: Haemoglobin ≥100 g/L and <UNL; neutrophil count ≥ 1 x 10  /L and <UNL; Platelet count ≥100 x 10  /L and <UNL; <2% immature myeloid cells ‡ and
	Clinical: Resolution of disease symptoms; spleen and liver not palpable; no evidence of EMH
PR	Peripheral blood: Haemoglobin ≥100 g/L and <UNL; neutrophil count ≥1 x 10  /L and <UNL; platelet count ≥100 x 10  /L and <UNL; <2% immature myeloid cells ‡ and
	Clinical: Resolution of disease symptoms; spleen and liver not palpable; no evidence of EMH or
	Bone marrow:* Age-adjusted normocellularity; <5% blasts; ≤grade 1 MF † , and peripheral blood: Haemoglobin ≥85 but <100 g/L and <UNL; neutrophil count ≥1 x 10  /L and <UNL; platelet count ≥50, but <100 x 10  /L and <UNL; <2% immature myeloid cells ‡ and
	Clinical: Resolution of disease symptoms; spleen and liver not palpable; no evidence of EMH
Clinical improvement (CI)	The achievement of anaemia, spleen or symptoms response without progressive disease or increase in severity of anaemia, thrombocytopenia, or neutropenia §
Anaemia response	Transfusion-independent patients: a ≥20 g/L increase in haemoglobin level  Transfusion-dependent patients: becoming transfusion-independent f

Response categories	Required criteria (for all response categories, benefit must last for ≥12 weeks to qualify as a response)
Spleen response	A baseline splenomegaly that is palpable at 5-10 cm, below the LCM, becomes not palpable** or
	A baseline splenomegaly that is palpable at >10 cm, below the LCM, decreases by ≥50%**
	A baseline splenomegaly that is palpable at <5 cm, below the LCM, is not eligible for spleen response
	A spleen response requires confirmation by MRI or computed tomography showing ≥35% spleen volume reduction
Symptoms response	A ≥50% reduction in the MPN-SAF TSS††
Progressive disease‡‡	Appearance of a new splenomegaly that is palpable at least 5 cm below the LCM or
	A ≥100% increase in palpable distance, below LCM, for baseline splenomegaly of 5-10 cm or
	A 50% increase in palpable distance, below LCM, for baseline splenomegaly of >10 cm or
	Leukaemic transformation confirmed by a bone marrow blast count of ≥20% or
	A peripheral blood blast content of ≥20% associated with an absolute blast count of ≥1 x 10  /L that lasts for at least 2 weeks
Stable disease	Belonging to none of the above listed response categories
Relapse	No longer meeting criteria for at least CI after achieving CR, PR, or CI, or
	Loss of anaemia response persisting for at least 1 month or
	Loss of spleen response persisting for at least 1 month

EMH, extramedullary haematopoiesis (no evidence of EMH implies the absence of pathology- or imaging study-proven non-hepatosplenic EMH); LCM, left costal margin; UNL, upper normal limit.

\*Baseline and post-treatment bone marrow slides are to be interpreted at one sitting by a central review process.

†Grading of MF is according to the European classification Thiele *et al.* European consensus on grading bone marrow fibrosis and assessment of cellularity. It is underscored that the consensus definition of a CR bone marrow is to be used only in those patients in which all other criteria are met, including resolution of leukoerythroblastosis.

‡Immature myeloid cells constitute blasts + promyelocytes + myelocytes + metamyelocytes + nucleated red blood cells. In splenectomized patients, <5% immature myeloid cells are allowed.

§See above for definitions of anaemia response, spleen response, and progressive disease. Increase in severity of anaemia constitutes the occurrence of new transfusion dependency or a ≥20 g/L decrease in haemoglobin level from pretreatment baseline that lasts for at least 12 weeks. Increase in severity of thrombocytopenia or neutropenia is defined as a 2-grade decline, from pretreatment baseline, in platelet or absolute neutrophil count, according to the Common Terminology Criteria for Adverse Events (CTCAE) version 4.0. In addition, assignment to CI requires a minimum platelet count of ≥25000 x 10^9/L and absolute neutrophil count of ≥0.5 x 10^9/L.

¶Applicable only to patients with baseline haemoglobin of <100 g/L.

‡Transfusion dependency before study enrollment is defined as transfusions of at least 6 units of packed red blood cells (PRBC), in the 12 weeks prior to study enrollment, for a haemoglobin level of < 85 g/L, in the absence of bleeding or treatment-induced anaemia. In addition, the most recent transfusion episode must have occurred in the 28 days prior to study enrollment. Response in transfusion-dependent patients requires absence of any PRBC transfusions during any consecutive “rolling” 12-week interval during the treatment phase, capped by a haemoglobin level of ≥ 85 g/L.

\*\*Spleen response must be confirmed by imaging studies where a  $\geq 35\%$  reduction in spleen volume, as assessed by MRI or CT, is required. Furthermore, a  $\geq 35\%$  volume reduction in the spleen, by MRI or CT, constitutes a response regardless of what is reported with physical examination.

††Symptoms are evaluated by the MPN-SAF TSS. The MPN-SAF TSS is assessed by the patients themselves and includes fatigue, concentration, early satiety, inactivity, night sweats, itching, bone pain, abdominal discomfort, weight loss, and fevers. Scoring is from 0 (absent/as good as it can be) to 10 (worst imaginable/as bad as it can be) for each item. The MPN-SAF TSS is the summation of all the individual scores (0-100 scale). Symptoms response requires  $\geq 50\%$  reduction in the MPN-SAF TSS.

‡‡Progressive disease assignment for splenomegaly requires confirmation by MRI or computed tomography showing a  $\geq 25\%$  increase in spleen volume from baseline. Baseline values for both physical examination and imaging studies refer to pretreatment baseline and not to post-treatment measurements.

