To ensure patient safety, a Data Safety Monitoring Committee (DSMC)/Safety Advisory Board (SAB) will perform reviews at least quarterly of safety parameters and pharmacodynamic markers to draw conclusions around the safety and pharmacodynamic effect of IMG-7289. Two sentinel patients were dosed sequentially at the original  $D_s$  of 0.25 mg/kg/d for 7 days and monitored twice-weekly before any additional patients were treated. The DSMC/SAB convened within 4 days post-completion of 7 days of treatment for each of the sentinel patients and determined it was safe for:

1. Each sentinel patient to continue dosing, and
2. Additional patients to begin treatment with IMG-7289.

Additionally, the DSMC/SAB convened post-completion of 7 days of treatment of the required three patients at the new  $D_s$  and determined:

1. The safety of the new  $D_s$ , and
2. The ITP Day 3 (mid-week) visit could be removed from the visit schedule.

This study initiated as a Phase 1/2a study, assessing the safety of the starting dose, an 85 day duration of treatment, and the pharmacokinetic and pharmacodynamic effects of IMG-7289, with transition to a Phase 2b study including implementation of changes supported by the Phase 1/2a data. This study consists of two treatment periods: The Initial Treatment Period (ITP), followed by the Additional Treatment Period (ATP). Patients are now enrolling in the Phase 2b portion of the study, in which patients are treated daily for 169 days in the ITP. In the ATP, which is iterative, treatment may continue for an additional 169 days in those patients deriving clinical benefit (defined as not meeting progressive disease criteria as per Section 16.7 and safely tolerating IMG-7289; this definition applies throughout the document and will not be repeated with each reference to clinical benefit), as determined by the Principal Investigator.

All patients will undergo follow-up period visits, including an End-of-Treatment (EoT) visit on the day of last dose or as soon as possible thereafter, a pre-End-of-Study (EoS) visit approximately 14 days post last dose, and an End-of-Study (EoS) visit approximately 28 days post last dose. Patients that do not enter the ATP, or discontinue early, will undergo follow-up, beginning with an EoT visit.

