### **6.8 Treatment Failure**

MF patients not deriving clinical benefit (defined as not meeting progressive disease criteria as per Section 16.7 and safely tolerating IMG-7289), or who achieve complete response (CR), partial response (PR) or clinical improvement (CI) and subsequently relapse (Section 16.7), the equivalent of treatment failures, will discontinue IMG-7289 and undergo the EoT, pre-EoS and EoS visits.

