### 8.2.3 Stopping Rules

IMG-7289 will be discontinued in the event of the following:

- Post DLT, the Medical Monitor and Principal Investigator deem it unsafe for the patient to continue on IMG-7289.
- Post dose reduction due to DLT, the patient fails to demonstrate significant improvement within 21 days.
- Post temporary interruption of IMG-7289 due to platelet counts below  $25 \times 10^9/L$  (25 k/ $\mu$ L), the patient's platelet counts don't return to  $> 50 \times 10^9/L$  (50 k/ $\mu$ L) within 21 days.

Patients who discontinue IMG-7289 will enter follow-up assessments beginning with EoT visit.

CCI

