## 9 STUDY ASSESSMENTS

This section provides comprehensive detail on the visits and assessments required; this section should serve as the main guidance for use during study visits. The Schedule of Assessments (Section 16.1) contains these details in schematic form, and is provided for use in a supportive/reference capacity only. In an effort to maintain clarity while facilitating a modicum of brevity, the 'Terms' in **Table 4** below will be utilized in this section to encompass the broader 'Protocol Meaning' as stated.

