### 9.5 Suspected Relapse

If at any time during the study a patient is suspected to have relapsed, *which can only occur post remission*, then a Suspected Relapse visit should be performed with the following assessments:

- Limited PE, including Vital Signs
- Adverse Events and Concomitant Medications
- Collect MPN-SAF TSS **7-DAY RECALL** tool
- Full Local Laboratory Assessment
- Urinalysis
- Blood samples for Central Laboratory genomic analysis\*
- Perform abdominal MRI or CT (if patient is not a candidate for MRI) within  $\pm 7$  days of visit, unless performed in the prior 5 weeks

**Note:** In Germany, use of computerised tomography (CT) is not permitted for patients unable to undergo magnetic resonance imaging (MRI). Only MRI is permitted for study purposes.

- Bone Marrow Sampling\* (unless performed in the last 21 days or is scheduled in next 7 days)

\*If possible, bone marrow and blood sampling for genomic analysis should be performed on the same day.

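### On assumed CTCAE platelet cut-points, a responder titrated into the platelet target can lose clinical improvement, which the protocol, read literally, treats as relapse and discontinuation (minor)

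*Protocol*

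**What the plan says.** Protocol 16.7 defines CI as "The achievement of anaemia, spleen or symptoms response without progressive disease or increase in severity of anaemia, thrombocytopenia, or neutropenia". Its footnote gives the platelet rule: "Increase in severity of thrombocytopenia or neutropenia is defined as a 2-grade decline, from pretreatment baseline, in platelet or absolute neutrophil count", graded by CTCAE version 4.0. The footnote attaches a 12-week duration to worsening anaemia but none to the platelet decline.

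The relapse row of 16.7 opens with "No longer meeting criteria for at least CI after achieving CR, PR, or CI". The one-month persistence requirement appears only in the other two relapse criteria, loss of anaemia response and loss of spleen response.

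Section 6.8 states the consequence for patients who reach CR, PR or CI: "clinical improvement (CI) and subsequently relapse (Section 16.7), the equivalent of treatment failures, will discontinue IMG-7289". Sections 5.1.1 and 5.1.2 say the same.

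Sections 5.1.1 and 7.2.3 set the titration target at 50-75 x 10^9/L. Inclusion criterion 8 requires at least 100 x 10^9/L at entry, so normal and high baselines are eligible.

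Three other passages bear on the same patient:
- Section 5.1 lets treatment continue while there is clinical benefit, "defined as not meeting progressive disease criteria as per Section 16.7 and safely tolerating IMG-7289". Platelet grade is not part of that test.
- The platelet stopping rule in 8.2.3 begins "Post temporary interruption of IMG-7289 due to platelet counts below" 25 x 10^9/L, and applies if counts do not recover above 50 within 21 days.
- Section 9.5 says of relapse, "which can only occur post remission", and Section 9 says of itself that "this section should serve as the main guidance for use during study visits".

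**The concern.** The dosing rules and the response rules pull in opposite directions. The first lower platelets into a set range; the second can count arrival in that range as a reason to withdraw a response category already held. Losing the category is relapse under 16.7, and relapse after CI is treatment failure under 6.8.

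At stake is the treatment of a patient whose spleen, symptom or anaemia response continues, whose platelets are where the titration aims, and who meets no stopping rule. Stopping is not neutral: Section 6.5 warns that platelets rebound after cessation and can exceed baseline. Sites could also handle the same patient differently, because 9.5 does not use the same terms as 6.8 and 16.7 for what relapse can follow.

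**Working it through.** The protocol prints no figure on this point to reproduce. The check has three parts.

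**1. Does a count in the target fail the CI platelet rule?**

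Inputs from the protocol: entry platelets at least 100; target 50-75; disqualifying change of two grades from baseline (all counts x 10^9/L). Assumed, because not printed: Grade 0 at or above the lower limit of normal (LLN), Grade 1 below LLN to 75, Grade 2 below 75 to 50, Grade 3 below 50 to 25; LLN between 100 and 150. Section 16.7 prints a CI platelet floor of 25000 x 10^9/L, an evident misprint, read here as 25; counts of 50-74 clear it.

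Grade change = grade on treatment minus grade at baseline; CI fails if this is 2 or more.

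| Baseline | Count on treatment | Grade change | CI platelet rule |
|---|---|---|---|
| At or above LLN (Grade 0) | 75 | 1 - 0 = 1 | met |
| At or above LLN (Grade 0) | 50, 60, 74 | 2 - 0 = 2 | fails |
| 100 to below LLN (Grade 1) | 50, 60, 74 | 2 - 1 = 1 | met |
| 100 to below LLN (Grade 1) | 49 | 3 - 1 = 2 | fails |

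The Grade 0 rows are the same for LLN of 100, 130, 140 and 150 and for baselines up to 800.

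Sensitivity to the assumptions, for a normal baseline:
- Grade 1/2 cut at 75: CI barred at 50-74. Cut at 70: 50-69. Cut at 60: 50-59. Cut at 50 or lower: no count in the target is barred.
- LLN of 130 leaves baselines of 100-129 unaffected at 50-74; LLN of 150 leaves 100-149 unaffected. With LLN at 100 or lower, every eligible baseline is exposed.

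**2. Does failing the rule lead to stopping?**

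Take a normal-baseline patient who has CI with platelets above target and is then titrated to 60.
- 16.7, CI: the two-grade decline means the criteria are no longer met.
- 16.7, relapse: no longer meeting at least CI is relapse. The exception is a patient who meets the second PR route, which accepts platelets from 50 to below 100 with the marrow, blood and clinical criteria; that patient is still above CI.
- 6.8, 5.1.1 and 5.1.2: relapse after CI leads to discontinuation.
- 5.1: the patient may still have clinical benefit. 8.2.3: a count of 60 triggers nothing.

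**3. How often could CI come before arrival in the target?**

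Only a patient who has held CI can lose it. A response must last 12 weeks (84 days). A symptom or anaemia benefit present from Day 7 gives CI at Day 7 + 84 = 91; from Day 28, Day 112. Benefit first shown on the Day 84 scan gives Day 84 + 84 = 168.

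Under Amendment 6 (Section 3.6.1), up-titrations can fall no earlier than Days 28, 49, 70, 91, 112, 133 and 154, and platelets settle 21-28 days after a dose is set. Section 5.1 puts the optimal dose for most patients at 0.6-0.8 mg/kg/d, from a start of 0.6. Step size is redacted; assume 0.1-0.5 mg/kg.
- To reach 0.8 in steps of 0.1: (0.8 - 0.6)/0.1 = 2 up-titrations, the last on Day 49, settled by 49 + 28 = Day 77. That is 91 - 77 = 14 days before the earliest CI. Larger steps finish sooner.
- For platelets to settle on or after Day 91, a third up-titration is needed (70 + 21 = 91). Up-titration number k is needed only for doses above 0.6 + (k - 1) x step, so for k = 3 above 0.8 (step 0.1) to above 1.6 (step 0.5).
- If CI comes at Day 112, a fourth is needed (91 + 21 = 112), for doses above 0.9 to above 2.1.

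So on the earliest permitted schedule most patients are not on this route in the Initial Treatment Period. Delayed up-titrations, or dose increases in the Additional Treatment Period, can still reach it. Amendment 5 patients (first up-titration Day 14) are not modelled, because their titration table is redacted.

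**The case against.** **The cut-point is outside the documents.** This stands as a condition. If the Grade 1/2 cut-point were 50 or lower, there would be no conflict within the target.

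**An exemption may sit in redacted text.** Titration Tables 1-3, the exploratory endpoints and the SAP response analyses are blacked out. A reader might infer that the plan contains no exemption; the documents support only that none is visible.

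**Investigators would not apply the rule this way.** Section 8.2.1 treats platelet reduction as an expected pharmacodynamic effect and not as adverse. Section 11 leaves the finding of treatment failure to the Investigator, and says the patient should then discontinue. A reader might infer an automatic stop from 6.8 alone; Section 11 does not support that. What remains is that the literal text of 6.8 points the other way.

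**CI might be judged only when assigned, or relapse might need persistence.** If the first relapse criterion acts at once, the one-month requirement has little work to do for a patient whose CI rests on a single spleen or anaemia response. That is a fair argument against acting on one count. It does not remove the problem: the relapse wording looks at whether criteria are still met, and titration is meant to hold platelets in the target, so the decline could well last a month.

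**Section 9.5 is not a true contradiction.** A reader might infer that 9.5 denies relapse after CI. The abbreviation list gives CR and PR as remission or response, the synopsis speaks of suspected relapse following response, and 9.5 schedules an assessment visit without ordering discontinuation. If 9.5 did exclude CI, the route described here would close for patients with CI only. The mismatch is mainly one of wording, but worth tidying.

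**The effect on results is slight.** Agreed. A reader might infer that the primary efficacy analysis is distorted; SAP VIII.A analyses spleen volume and spleen size directly and does not use the CI platelet rule.

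**Conclusion.** The point holds in a conditional and narrow form, as a minor issue. It requires all of the following:
- a Grade 1/2 platelet cut-point above 50 x 10^9/L (75 assumed);
- a baseline at or above LLN;
- CI held while platelets are above target;
- later titration to 50-74 (with the cut at 75) without PR.

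For that patient, 16.7 and 6.8 taken literally say relapse and discontinuation while the response continues, the count is on target and 8.2.3 is not met.

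A reader might infer that titration to target generally forces responders off drug. The documents do not support that. Baselines from 100 to below LLN are unaffected at 50-74, patients already in target before 12 weeks of benefit never hold CI to lose, and at 0.6-0.8 mg/kg/d the earliest-schedule arithmetic puts arrival in target before the earliest possible CI. How many patients would be affected cannot be derived from the documents.

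**What to change.** Add to 6.8, with cross-references in 5.1.1 and 5.1.2:

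*Loss of CI solely because of a platelet decline to a count that remains at or above 50 x 10^9/L during protocol titration, with the spleen, symptom or anaemia response maintained, is not relapse or treatment failure and does not require discontinuation.*

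The floor of 50 matters. Tying the exemption only to 8.2.3, whose platelet rule starts below 25, would also excuse counts of 25-49, which are under the dosing target. Counts below 50 stay under the titration, dose-hold and 8.2.3 rules.

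In 9.5, replace *post remission* with *after CR, PR or CI*, to match 6.8 and 16.7. Leave 16.7 as printed.

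The cost is one sentence, two cross-references and one wording change, with no new data and no change to dosing or endpoints. The downside is that the protocol's discontinuation rule departs slightly from the published relapse criteria.

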### 5.1.2 Additional Treatment Period (ATP) for Qualifying Patients Only

For the purposes of clarity and efficiency, rather than continuing to present chronological days/weeks, visits are presented as 'ATP Day 0', followed by, 'ATP Days 28, 56, 84', etc. Qualifying patients will 're-start' IMG-7289 on ATP Day 0, with dose titration continuing as per the Titration Rules table (Section 7.2.3.2); there should be no interruption in dosing (Day 168 = Day 0 of the next ATP). Additional dose-titration may occur in consultation with the Medical Monitor.

During the ATP, qualifying patients will return to the clinic monthly for study assessments (ATP Days 0, 28, 56, 84, 112, 140 and 168). It is anticipated that patients continuing in the ATP will have already achieved a stable dose, with bi-weekly visits no longer necessary. For the exceptional patient whose dose has not stabilized, bi-weekly visits may continue at the PI's discretion. On Day 168, patients will undergo the same procedures and assessments as per ITP Day 168, including MRI or CT (if patient is not a candidate for MRI), and bone marrow sampling. Prior to or at the Day 168 visit, but ideally at the Day 140 visit for logistical purposes, a 'qualification' assessment will again be made to determine whether the patient is continuing to derive clinical benefit, thereby re-qualifying for continued treatment in the ATP. The ATP is iterative and may repeat (ATP1, ATP2, etc.), without interruption in dosing, as long as the patient continues to qualify.

**Note:** In Germany, use of computerised tomography (CT) is not permitted for patients unable to undergo magnetic resonance imaging (MRI). Only MRI is permitted for study purposes.

Patients not deriving clinical benefit, or who achieve CR, PR or CI and subsequently relapse (Section 16.7), the equivalent of treatment failures, will discontinue IMG-7289 and undergo EoT, pre-EoS and EoS visits.

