### 6.1.1 Inclusion Criteria

Patients must meet all of the applicable criteria to be eligible for enrollment in this study:

1. Willing and able to sign the approved informed consent.
2. Age: 18+ years old at Screening.
3. Diagnosis of either PMF per World Health Organization (WHO) diagnostic criteria for myeloproliferative neoplasms (Section 16.2), PPV-MF per the IWG-MRT (Section 16.3), or PET-MF per the IWG-MRT (Section 16.4) and meet the following additional subtype specific criteria:
  - a. Classified as high risk (3 prognostic factors), intermediate risk-2 (2 prognostic factors) or intermediate risk-1 (1 prognostic factor). The prognostic factors, defined by the International Working Group ([Cervantes, et al., 2009](#)):
    - i. Age > 65 years;
    - ii. Presence of constitutional symptoms (weight loss, fever, night sweats);
    - iii. Marked anaemia (Hgb < 10g/dL)\*;
    - iv. **History** of leukocytosis [WBC > 25 x10^9/L (25,000/μL)];
    - v. Circulating blasts ≥ 1%.

\*A haemoglobin value < 10 g/dL must be demonstrated during Screening for patients who are not transfusion dependent. Patients receiving regular transfusions of packed red blood cells will be considered to have haemoglobin < 10 g/dL for the purpose of evaluation of risk factors.
4. Be refractory or resistant to, inadequately controlled by or intolerant of available approved therapy, or in the Investigator's judgment, are not candidates for available approved therapy (note: approved therapy includes ruxolitinib and, in the US, fedratinib).
5. Eastern Cooperative Oncology Group (ECOG) performance status score ≤2.
6. Peripheral blast count ≤10% prior to dosing on Day 0.
7. Absolute neutrophil count ≥ 0.5 x 10^9/L (500/μL) prior to dosing on Day 0.
8. Platelet count ≥ 100 x 10^9/L (100 k/μL) prior to dosing on Day 0.
9. Life expectancy >36 weeks.

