#### 6.5 Guidelines

Patient safety is paramount. The guidelines provided below are intended to provide some consistency across sites by providing guidance to be used by the Investigator, the study staff and the patient to safeguard patient safety while maintaining data integrity. The guidelines are not intended to supersede best clinical judgment by the Investigator. Please contact the Medical Monitor with questions or with planned/known divergences from these guidelines.

1. In general, supportive care (transfusions, administration of anti-fungals, etc.) should be maintained in accordance with institutional policy. Additionally:
  - a. It is advised that patients with a platelet count  $\leq 10 \times 10^9/L$  (10 k/ $\mu L$ ) be transfused.
2. Hydroxyurea may be used during the study in case of proliferation as follows:
  - a. At the PI's discretion, initiate hydroxyurea treatment for white cell count  $\geq 30 \times 10^9/L$  (30,000/ $\mu L$ ) and majority of cells appear to be immature cells (myelocytes/ promyelocytes)
  - b. Discontinue hydroxyurea treatment when white cell count is  $< 10 \times 10^9/L$  (10,000/ $\mu L$ )
3. Patients taking medications that have the potential to induce or inhibit CYP3A4 or CYP2D6 should be monitored closely for potential effects of co-administration; particular attention should be given to anti-infectives in the azole class.
4. Cessation of IMG-7289 is invariably associated with a rebound in thrombopoiesis and the platelet count can easily exceed the baseline value in any given patient. When IMG-7289 is discontinued, the platelet count should be monitored closely and the timing of the start of an alternative therapy should take this into account.

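### Protocol 16.7 prints the platelet floor for clinical improvement 1000 times too high; read literally, no patient can be classed as CI, and one of the three relapse criteria depends on CI

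*Protocol*

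**What the plan says.** Protocol 16.7 defines CI as an anaemia, spleen or symptom response without progression or worsening cytopenia. A footnote (§) adds two laboratory floors. For platelets it says "assignment to CI requires a minimum platelet count of ≥25000 x 10", the power and unit being 10⁹/L. For neutrophils, in the same sentence, the floor is 0.5 × 10⁹/L.

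The same table sets the platelet requirement for complete response (CR) as "Platelet count ≥100 x 10", also in units of 10⁹/L. Partial response (PR) has two routes. One needs platelets of at least 100. The other, which needs a marrow response, takes platelets from 50 to below 100 and haemoglobin from 85 to below 100 g/L.

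Relapse has three alternative criteria. The first reads "No longer meeting criteria for at least CI after achieving CR, PR, or CI, or". The other two are loss of an anaemia response, or of a spleen response, lasting a month or more.

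Section 5.1.2 states that patients "who achieve CR, PR or CI and subsequently relapse (Section 16.7), the equivalent of treatment failures, will discontinue IMG-7289". Sections 5.1.1 and 6.8 say the same.

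**The concern.** The floor is part of an operative definition, so it matters more than a slip in background text. As printed, the lowest response category needs far more platelets than the highest, and more than any patient can have. Two things would follow from literal use.

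- A patient could be counted as relapsed, and so taken off drug, while still holding a response that the protocol means to recognise.
- Any programmed response derivation that copied the line would return no CI at all.

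**Working it through.** **Units.** One litre is 10⁶ µL, so a count per µL is the 10⁹/L value × 10⁹ / 10⁶.

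- Printed floor: 25000 × 10⁹ / 10⁶ = 25,000,000/µL (25,000 k/µL).
- For comparison: 25 × 10⁹ / 10⁶ = 25,000/µL (25 k/µL).
- Ratio: 25000 / 25 = 1000.

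**The protocol's own unit pairs.** Where the protocol prints a cell count in both units, the pairs agree:

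| Protocol section | Cell | 10⁹/L | Per µL, as printed |
|---|---|---|---|
| 6.1.1, criterion 3 | white cells | 25 | 25,000/µL |
| 6.1.1, criterion 7 | neutrophils | 0.5 | 500/µL |
| 6.1.1, criterion 8 | platelets | 100 | 100 k/µL |
| 6.5 | platelets | 10 | 10 k/µL |
| 6.6 | platelets | 50 | 50 k/µL |
| 8.2.3 | platelets | 25 | 25 k/µL |
| 16.7, CI footnote | platelets | 25000 | not given |

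Two rows point to the source of the slip. Criterion 3, "of leukocytosis [WBC > 25 x10"⁹/L, gives 25,000/µL as its equivalent, and that is the number that appears in 16.7 with the wrong unit. The stopping rule beginning "Post temporary interruption of IMG-7289 due to platelet counts below" uses 25 × 10⁹/L as a platelet level. The neutrophil floor beside the CI platelet floor, 0.5 × 10⁹/L, is on the right scale and matches criterion 7.

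**Size against the other platelet limits.**

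- CR minimum and entry minimum: 25000 / 100 = 250 times.
- Lower end of the titration target (also the marrow-route PR minimum): 25000 / 50 = 500 times.
- Upper end of the titration target: 25000 / 75 ≈ 333 times.

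**What changes under literal reading.** Take patients who meet every other CI condition and have platelets of at least 25 × 10⁹/L.

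| Patient | Floor 25000 (printed) | Floor 25 (inferred) |
|---|---|---|
| Lost CR or PR, keeps a spleen, anaemia or symptom response | Below CI, so relapse by the first criterion | CI, not relapse by that criterion |
| Never CR or PR, has a spleen, anaemia or symptom response | Stable disease | CI |
| As the row above, response in symptoms only, later lost | No relapse criterion met | Relapse by the first criterion |
| Still in CR or PR | No change | No change |
| Never had any response | Stable disease | Stable disease |

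Wrongful stopping is therefore limited to the first row. In the second and third rows the error runs the other way: a response goes unrecorded, and its loss may not be recognised as relapse.

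**How many could be in the first row.** Dosing aims for 50–75 × 10⁹/L (Sections 5.1.1 and 7.2.3). CR and one PR route need at least 100, so a patient at target can reach only the marrow-route PR, with haemoglobin in its 85 to below 100 g/L band, and must hold it for 12 weeks. The documents give no response rates, so no frequency can be computed.

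**The case against.** The strongest reply is that this is an editorial erratum. A plausible wrong threshold can be misapplied without anyone noticing; an impossible one cannot. The titration target, the CR and PR limits and the stopping level all show the intended scale. Treatment failure is the investigator's determination (Section 11), and a suspected relapse triggers a visit with laboratory tests, imaging and marrow (Section 9.5). Entry to the Additional Treatment Period rests on absence of progression and on tolerability, not on CI. This stands as a limit on the consequences. It does not make the printed line correct, and no visible text corrects it.

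A reader might infer that CI alone defines relapse. It does not: the two criteria on loss of anaemia or spleen response do not use the platelet floor. They are alternatives, however, so they do not rescue a patient who meets the first.

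A reader might also infer that the trial's response tables will show no CI. The documents do not support that. The SAP mentions tests on response (VI) and a not-evaluable category (VI.K), but the detailed response analyses are redacted and may state a workable value.

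Finally, the same footnote bars CI after a two-grade platelet fall from pretreatment. Some patients would miss CI whatever the floor, which further narrows the group affected by this figure alone.

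**Conclusion.** The platelet floor for CI is wrong as written, by a factor of 1000, and makes CI unattainable on a literal reading. It reaches a treatment decision through the first relapse criterion and the requirement to stop drug on relapse.

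The practical effect is probably small. It depends on someone applying 25 million per µL at face value, and wrongful stopping also requires a patient who has lost CR or PR while keeping a lesser response. A reader might infer that the primary results are at risk; they are not on this account. The visible spleen volume and spleen size analyses (SAP VIII.A) and the safety analyses (SAP IX) make no use of CI.

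The conclusion that the printed figure is wrong rests on the protocol's own limits. The replacement value of 25 × 10⁹/L is an inference: it fits the unit pairs and the stopping rule, but the documents do not state it for CI.

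**What to change.** In the CI footnote of Protocol 16.7, replace the platelet floor with ≥25 × 10⁹/L (25 k/µL), after the sponsor confirms that this is the intended value. Printing both units, as the protocol does for its other platelet limits, would guard against a repeat. Use the confirmed value in any derivation of CI or relapse.

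The cost is a one-line correction, with no new data, visits or analyses. Section 14.1 already allows ethics committees to handle minor changes by expedited review.
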